4.12 Efficacy of Pembrolizumab in Lung Cancer

The safety and efficacy of PD 1 inhibition with pembrolizumab in patients with advanced non-small cell has been investigated in a phase I clinical trial (48). Four hundred and ninety five patients with advanced NSCLC were treated with pembrolizumab (at a dose of either 2mg or 10mg per kilogram every 2 weeks or 10 mg per kilogram every 2 weeks). Treatment-related adverse events occurred in 351 patients (70.9%), with no clear difference according to dose or schedule. The most common treatment-related adverse events were fatigue, pruritus, and decreased appetite. Adverse events of grade 3 or higher were reported in 47 of 495 patients (9.5%). The only treatment-related adverse events of an inflammatory or immune-mediated nature that occurred in more than 2% of patients were infusion-related reactions (in 15 patients [3.0%]), hypothyroidism (in 34 patients [6.9%]), and pneumonitis (in 18 patients [3.6%]). One infusion reaction led to treatment discontinuation. All the patients with hypothyroidism were successfully treated with medical therapy. Pneumonitis of grade 3 or greater was observed in 9 patients (1.8%), including 1 (0.2%) who died. The overall response rate was 19.4% (95% confidence interval [CI], 16.0 to 23.2), which included a response rate of 18.0% (95% CI, 14.4 to 22.2) in the 394 previously treated patients and 24.8% (95% CI, 16.7 to 34.3) in the 101 previously untreated patients. The best overall response was stable disease in 21.8% of patients. The response rate was similar regardless of dose, schedule, and histologic analysis.

At the time of this analysis, 84.4% of patients with a response had no disease progression, and the median duration of response was 12.5 months (range, 1.0 to 23.3) in all patients, 10.4 months (range, 1.0 to 10.4) in previously treated patients, and 23.3 months (range, 1.0 to 23.3) in previously untreated patients. Median progression-free survival was 3.7 months (95% CI, 2.9 to 4.1) for all the patients, 3.0 months (95% CI, 2.2 to 4.0) for previously treated patients, and 6.0 months (95% CI, 4.1 to 8.6) for previously untreated patients. Median overall survival was 12.0 months (95% CI, 9.3 to 14.7) for all the patients, 9.3 months (95% CI, 8.4 to 12.4) for previously treated patients, and 16.2 months (95% CI, 16.2 to not reached) for previously untreated patients.

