12.3 Serious Adverse Event Definition

Adverse events and adverse drug reactions are considered 'serious' if they threaten life or function.

Due to the significant information they provide, serious adverse events (SAE) (including Serious Adverse Drug Reactions) require expedited reporting. SAEs are defined as any adverse event or adverse drug reaction which:

- Results in death (i.e. fatal/grade 5 CTCAE)
- Is life-threatening (i.e. grade 4 CTCAE)
- Requires inpatient hospitalisation or prolongation of existing hospitalisation
- Results in persistent or significant disability/incapacity; or
- Is a congenital anomaly/birth defect
- Is a new cancer (that is not a condition of the study)
- Is associated with an overdose
- Other significant medical event*

*Medical and scientific judgment should be exercised in deciding whether expedited reporting is also appropriate in other situations, such as important medical events that may not be immediately life threatening or result in death or hospitalization but may jeopardize the patient or may require intervention to prevent one of the other outcomes listed in the definition above. These should usually be considered serious.

The following are NOT considered SAEs:

- Hospitalizations not intended to treat an acute illness or adverse event (e.g., social reasons such as pending placement in long-term care facility).
- Surgery or procedure planned before entry into the study. Note: Hospitalizations that were planned before the signing of the PICF, and where the underlying condition for which the hospitalization was planned has not worsened, will not be considered serious adverse events. Any adverse event that results in a prolongation of the originally planned hospitalization is to be reported as a new serious adverse event.
- Disease progression should NOT be reported as an adverse event or serious adverse event term; instead, signs and symptoms of clinical sequelae resulting from disease progression/lack of drug efficacy will be reported if they fulfill the serious adverse event definition.
- A standard procedure for protocol therapy administration will not be reported as a serious adverse event. Hospitalization or prolonged hospitalization for a

complication of therapy administration will be reported as a serious adverse event.

- The administration of blood or platelet transfusion. Hospitalization or prolonged hospitalization for a complication of such transfusion remains a reportable serious adverse event.

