12.8 Serious Adverse Event Reporting

12.8.1 Trial sites/investigators

All SAEs that occur from the time a patient has signed consent for the Trial to within 30 days of the final protocol-specified treatment are required to be reported to the Sponsor whether or not considered related to the treatment under investigation.

The Principal Investigator (PI) must:

- Determine whether an AE is 'Serious'
- For SAEs, the PI must then ascertain the suspected cause
- The attribution to the SAE must be recorded in the patients' medical records and reported on the SAE form.

SAEs must be reported by completing the SABRseq SAE form and emailing/faxing to the following:

Sponsor (or delegate)	[contact]
Merck Global Safety	[contact]
Merck Canada INC	[name] or [contact]

SAE forms are required at the following points:

Initial Report	Within one working day/24 hours of discovery or notification of the event. If the reporting of an SAE is delayed by more than 24 hours, an explanation must be provided on the SAE form.
Incomplete Reports	If all details are not available at the time of the initial report a completed report must be sent within the next 10 days.
Updated Report	If the event is not resolved (or 'on-going') at the time of the initial report, the SAE Form must be submitted every 30 days until the event is resolved, death has occurred or the condition has stabilised. If a change occurs in a stable condition (i.e. either worsens or improves), then a new SAE Form should be faxed

The Investigator is ultimately responsible for reporting the SAE and must sign the final SAE report(s). Should this Investigator not be available to sign the initial SAE form within the 24-hour period, a comment to this effect must be written on the form and the form signed by

the clinician attending to the patient at the time and faxed to the Sponsor. The investigator must sign the SAE form as soon as possible and re-fax to the Sponsor.

The Investigator at the Trial Site is responsible for determining the local SAE reporting requirements of the responsible HREC and subsequently notifying the HREC of SAEs as required.

All SAEs that have not resolved by the end of the study, or that have not resolved upon discontinuation of the patients participation in the study, must be followed until any of the following occurs:

- The event resolves
- The event stabilizes
- The event returns to baseline, if a baseline value/status is available

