14.5 Safety Analysis

Safety will be assessed using CTCAE v4.03 and the maximum toxicity grade per patient of each adverse event will be derived and presented in table format according to arm and overall. The number of patients who suffer from grade 3 or higher toxicities (for each toxicity type and overall) will be provided considering all patients who have received at least one dose of pembrolizumab and completed at least one SABR treatment. The safety analysis will be conducted twice: once for all AE's, regardless of relatedness to treatment and once considering only AE's related to the treatment (i.e. classified as possibly, probably or definitely related).

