14.10 Early Termination Criteria

Consideration of suspension of patient accrual will occur if an unacceptable rate of toxicity is detected. The expected rates of grade 3+ pneumonitis and colitis are expected to be less than 5%. If at any given time during the trial 3 or more patients present with treatment related pneumonitis or colitis of grade 3-4 toxicity, data will be reviewed by the TMC and consideration will be given to permanently suspend recruitment and close the trial

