17.3 Trial Management Committee (TMC)

The TMC will initially meet to assess safety after 3 patients in each arm has completed 8 cycles of pembrolizumab. Thereafter, the TMC will meet at 6 monthly intervals.

The TMC will comprise the following members:

- Radiation Oncology Principal Investigator
- Medical Oncology Principal Investigator
- An Independent Research Physician
- Clinical Trial Manager
- Trial Statistician

The C/PI will receive and review SAEs in real time.

The TMC will receive periodic safety reports therefore facilitating a response to potential safety issues. The TMC will also oversee study planning, monitoring, progress, review of information from related research, and implementation of recommendations from other study committees and external bodies (e.g. ethics committees). The primary mandate of the TMC would be to protect patient safety. If adverse events of a particularly serious type are more common than anticipated, the study can be considered for termination. Please see SABRseq TMC terms of reference for further information.

The TMC will consider whether to continue the study as planned, modify, or stop it, based on reports provided by BaCT or other information.

18. Publication and Presentation Policy

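### Section 14.10 sets its benchmark for grade 3+ pneumonitis and colitis, but its three-patient trigger counts only grade 3-4, so read literally a case recorded as grade 5 is not counted

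*Combined protocol and SAP*

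**What the plan says.** Section 14.10 (Early Termination Criteria) puts two grade ranges in consecutive sentences. The benchmark sentence reads "The expected rates of grade 3+ pneumonitis and colitis are expected to be less than 5" per cent. The trigger sentence says that if at any given time "3 or more patients present with treatment related pneumonitis or colitis of grade 3-4 toxicity, data will be reviewed by the TMC", and permanent closure of recruitment will then be considered.

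Three other places bear on the reading:

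- Section 12.3 (Serious Adverse Event Definition) lists "Results in death (i.e. fatal/grade 5 CTCAE" separately from life-threatening events, which it assigns to grade 4. In this protocol, then, grade 5 is not part of grade 4.
- Section 14.5 (Safety Analysis) derives the maximum grade per patient for its tables and reports "The number of patients who suffer from grade 3 or higher toxicities". That range has no upper limit.
- Section 4.12 shows that fatal cases are foreseeable. In the cited phase I study of pembrolizumab in 495 patients, "Pneumonitis of grade 3 or greater was observed in 9 patients (1.8%), including 1 (0.2%) who died".

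Nothing in the supplied text says that a grade 5 case counts towards the three patients.

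**The concern.** The benchmark and the trigger concern the same two toxicities, and the natural purpose of the trigger is to flag a rate above the benchmark. Read literally, the two do not count the same cases. The trigger leaves out the fatal ones, which matter most. For example, two patients with grade 3 pneumonitis and a third whose pneumonitis is recorded only as grade 5 would make three grade 3+ patients but only two towards the trigger.

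This is the only rule in the plan that counts toxicities across the whole trial. (Table 7 and section 12.9 also contain thresholds, but for individual patients.) At stake is whether the committee is called by rule or by discretion when one of the qualifying cases is a death, and whether the people applying the rule have to interpret it for the first time after a death.

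**Working it through.** **1. The wording, side by side**

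| Place | Purpose | Grade range | Includes grade 5? |
|---|---|---|---|
| 14.10, benchmark sentence | Expected rate, below 5% | 3+ | Yes |
| 14.10, trigger sentence | Committee review at 3 or more patients | 3-4 | No, read literally |
| 14.5 | Safety tables | 3 or higher | Yes |

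The trigger is the only one of the three that stops at grade 4. The finding rests on this comparison. The arithmetic below only shows its size.

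**2. The plan's own figures**

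The plan gives no operating characteristics for the trigger, so there is no trigger figure to reproduce. The nearest stated figures are in Table 9 (section 14.9), the probability of at least one patient with a toxicity, 1 - (1 - p)^n:

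- p = 5%: 1 - 0.95^16 = 0.560 and 1 - 0.95^32 = 0.806.
- p = 10%: 1 - 0.90^16 = 0.815 and 1 - 0.90^32 = 0.966.

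These match Table 9, so the same binomial model is used for the trigger.

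**3. Inputs for the illustration**

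- n = 32 patients (section 14.9).
- True rate p of grade 3+ pneumonitis or colitis, as one combined rate: 5%, the edge of what 14.10 expects, and 10%, a rate that a safety trigger should notice. Both are assumptions.
- Fatal share f of grade 3+ cases: 1/9, from one death among nine cases in section 4.12. This comes from pneumonitis on pembrolizumab alone, and applying it to colitis is an assumption. The exact 95% interval for 1/9 is 0.3% to 48%.
- Each patient is classed by maximum grade. This too is an assumption: 14.5 specifies it for its tables, but 14.10 does not.

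**4. Probability of reaching the trigger**

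P(X ≥ 3) = 1 - P(0) - P(1) - P(2), with X binomial on 32 patients. The rate is p if grade 5 counts, and p(1 - f) = 8p/9 if it does not.

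- p = 5%, grade 5 counted: 1 - 0.1937 - 0.3263 - 0.2662 = 0.214.
- p = 5%, grade 5 not counted (rate 4.44%): 1 - 0.2334 - 0.3475 - 0.2505 = 0.169.
- p = 10%, grade 5 counted: 1 - 0.0343 - 0.1221 - 0.2103 = 0.633.
- p = 10%, grade 5 not counted (rate 8.89%): 1 - 0.0508 - 0.1587 - 0.2401 = 0.550.

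The loss is about 5 percentage points at a 5% rate and 8 at a 10% rate.

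**5. Sensitivity**

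- Over the interval for f (0.3% to 48%), the probability under the literal wording runs from 0.213 down to 0.049 at p = 5%, and from 0.631 down to 0.229 at p = 10%. One death says little about f.
- If every fatal case first presents at grade 3-4 and is counted at that point, the loss is zero whatever f is.

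**The case against.** The strongest reply is that the wording changes little in practice. The trigger leads only to a review and to consideration of closure, and both can be reached without any grade limit. The opening sentence of 14.10 covers any unacceptable toxicity rate, and section 17.3 lets the committee consider termination if particularly serious events are more frequent than anticipated. A death is a serious adverse event, reportable "Within one working day/24 hours of discovery or notification of the event" (section 12.8.1), and section 17.3 adds "The C/PI will receive and review SAEs in real time". This stands, and it is why the point is small. These routes are discretionary or deal with individual cases, however, and none of them adds grade 5 to the count.

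Second, 14.10 speaks of patients presenting with the toxicity at any time, which fits a running count. On that reading, a patient seen at grade 3 or 4 who later dies is already counted. This is a fair reading, and 14.10 does not rule it out. It confines the gap to cases recorded only as grade 5, or to a count made by maximum grade.

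Third, the purpose of the trigger is inferred, since 14.10 gives no derivation for the three patients, and 14.5 is a reporting table that need not match a monitoring rule. Both remarks are correct, but the mismatch within 14.10 remains without 14.5.

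A reader might go further and infer that a treatment-related death could pass without review, or that the plan is deficient because it has no separate rule for deaths. The documents do not support either. The reporting routes above cover deaths, and on the committee's working rules section 17.3 says "Please see SABRseq TMC terms of reference for further information". Those terms were not supplied, so nothing can be concluded about what they require after a death.

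**Conclusion.** The point holds as a minor inconsistency in wording: the trigger in 14.10, read literally, omits grade 5 cases that its own benchmark includes. It is probably a drafting slip.

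The textual finding needs no assumption. The size does: the figures of 17% rather than 21%, and 55% rather than 63%, require the 1/9 fatal share for both toxicities, classing by maximum grade, and one combined rate over all 32 patients. They illustrate the effect and do not estimate it. For a given fatal share they lie towards the upper end of the loss, because any fatal case counted earlier at grade 3-4 reduces it, possibly to nil. The finding does not show that deaths escape safety oversight.

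**What to change.** In section 14.10, replace grade 3-4 in the trigger sentence with grade 3 or higher. The trigger then matches the benchmark sentence before it and the range used in 14.5, and it no longer matters whether a fatal case is counted when it first presents or by its maximum grade.

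The cost is one changed grade range, with no new committee, data or reporting. The downside is slightly more frequent committee reviews: under the assumptions above, in about 5% more trials at a 5% true rate (21.4% - 16.9% = 4.5 points) and 8% more at a 10% rate (63.3% - 55.0% = 8.3 points). None of these reviews stops the trial automatically.

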14.11 Deviations

Any deviations from the statistical plan should be described and justified in the protocol (i.e. protocol amendment) or in the statistical report.

15. Trial Management & Administrative Requirements

15.1 Trial Personnel

The Investigator(s) is responsible for ensuring that all trial personnel are qualified for their designated roles and provides information about the trial to all staff members involved in the trial or any element of patient management, both before starting the practical performance of the trial and during the course of the trial (e.g. when new staff become involved).

Additional information available during the trial should be given, as agreed upon, either by the investigator or delegate and always when a new staff member becomes involved in the trial.

15.2 Audit and Inspection

According to ICH/GCP Guidelines, the Sponsor may audit the investigational site to compare raw data, source data and associated records with the interim (if applicable) or final report of the trial to assure that data have been accurately reported. The Sponsor's Clinical Quality Assurance department is responsible for the auditing of the trial. Auditing may be contracted to an external body.

The Investigator(s) must accept that regulatory authorities may conduct an inspection to verify compliance of the trial with GCP.

15.3 Protocol Deviations

The protocol must be read thoroughly and the instructions must be followed. However, exceptions will be made in emergency situations when the protection, safety and wellbeing of the patient requires immediate intervention based on the judgement of the Investigator or a responsible, appropriately trained and credentialed professional(s) designated by the

Investigator as a sub-investigator.

In the event of a significant deviation due to an emergency, accident or error, the Investigator or designee must contact the Principal Investigator and notify the Sponsor (OCR) at the earliest possible time by telephone. This allows for an early joint decision to be made as to whether or not the patient should continue in the trial.

16. Data Handling and Record Keeping

16.1 Case Record Form (CRF)

In this trial the CRF will be electronic (eCRF). The investigator or the designated site person must complete the CRF and supporting documentation for each patient within a timely manner of the visit occurring.

The Clinical Trial Manager(s) will review the completed data for accuracy, completeness and consistency. The Clinical Trial Manager will submit requests for correction / clarification of data (e.g. queries) to the Investigator or designee when inconsistencies are identified during review, monitoring (if applicable) or during the edit check process.

All corrections and alterations to CRF data must be made by the investigator or by the designated site personnel in a timely manner and in accordance to the instructions provided. Completed CRFs should be reviewed and signed by the Principal Investigator or designated site personnel. All persons appointed by the Investigator to participate in the trial must be indicated on the delegation of authority log.

16.2 Source Documents

The investigator is required to prepare and maintain adequate and accurate case histories (i.e. medicals) designed to record all observations and other data pertinent to the trial for each trial patient. The medical records must contain adequate information to allow for verification of patient identity throughout the trial.

Any date recorded directly on the CRF, as agreed by the Sponsor for which no other written or electronic record will be maintained in the patient's medical record, will be considered source data (e.g. results from physical examinations, vital signs testing or the drug administration procedure).

The eCRF and the patient's medical records pertinent to the trial may be reviewed by a designated monitor, auditors and possibly by representatives from the IRB/IEC and regulatory bodies such as the TGA, US Food and Drug Administration (FDA) or the Canadian Health Authority to the extent permitted by regulation.

The investigator is required to retain a patient identification code list to allow unambiguous identification of each patient included in the trial. This list should contain the patient's full name, date of birth, and dates of participation and trial identification number. This list is

held in confidentiality at the Investigator site.

Source documents pertaining to the trial must be maintained by investigational sites and de-identified copies provided to BaCT in accordance with the source data verification checklist (provided by BaCT). Source documents should include a patient's medical records, hospital charts, clinic charts, the investigator's patient study files, as well as the results of any diagnostic tests such as x-rays, CT/MRI scans, laboratory tests, ECGs etc.

16.3 Archiving of Trial Documents

Trial data and other essential documentation must be retained for a period of at least 15 years (MHRA Guidelines).

It is the responsibility of the Sponsor to inform the Investigator(s) / site(s) when these documents need no longer be retained. The original record of CRFs will be archived by the Sponsor for at least 15 years. No trial document or image will be destroyed without prior written agreement between the Sponsor and the Investigator(s). Should the Investigator(s) wish to assign the trial records to another party or move to another location, advance written notice will be given to the Sponsor.

17. Ethical Aspects

17.1 Informed Consent

This trial will be conducted in compliance with 21 CFR Part 50 for informed consent. Written informed consent will be obtained from each patient before any procedures or assessments are done and after the aims, methods, anticipated benefits, and potential hazards are explained. Explanation will also be provided to the patients that they are free to refuse entry into the trial and free to withdraw from the trial at any time without prejudice to future treatment.

The patient's willingness to participate in the trial will be documented in writing on a consent form, which will be signed by the patient with the date and time of that signature indicated. The Investigator(s) will keep the original consent forms and copies will be given to the patient. In addition, the process of obtaining consent will be documented in the patient's medical record by the person conducting the informed consent discussion.

Written and/or oral information about the trial in a language understandable by the patient will be given to all patients. The information provided must include an adequate explanation of the aims, methods, anticipated benefits, potential hazards, and insurance arrangements in force.

